7.3 Reporting of SUSARs/ Expedited Reporting of Unexpected Serious ADRs

The sponsor will via coordinating CRO ensure the notification of the appropriate ethics committees, competent authorities and participating investigators of all SUSARs events occurring at the sites in accordance with local legal requirements, statutes and the European Clinical Trial Directive as follows:

- Reporting of the SUSAR to the Competent Authorities and Ethics Committees within 15 days (or within 7 days for fatal and life-threatening events)
- Sending the event to all participating Investigators for information (with confirmation of receipt).
- In addition, all events that require a new assessment of the risk-benefit ratio will be reported to the Ethics Committee and the Competent Authority of each concerned Member State within 15 days. This includes:
 - Single reports of expected serious adverse reactions with unexpected outcome.
 - An increase in the rate of occurrence of expected serious adverse reactions which is judged to be clinically relevant
 - Post-study SUSARs that occur after the patient has completed a clinical trial
 - New events related to the conduct of the trial or the development of the investigational medicinal products and likely to affect the safety of the subjects

The sponsor is responsible to ensure that the latest investigator's brochure is used as the source document for determining the expectedness of an SAE.

7.4 Recording of Adverse Events

The investigator is responsible for ensuring that all adverse events observed by the investigator or reported by subjects are properly recorded in the subjects' medical records and the electronic case report form.

The following adverse event attributes must be assigned by the investigator:

- Adverse event term according to the NCI-CTC criteria Version 4.03
- Severity grade according to the NCI-CTC criteria Version 4.03
- Start date and stop date (or date of last assessment)
- Outcome
- Causality to study drug and chemotherapy (to be assessed as either related or unrelated)
- Any action taken

Adverse events will be followed until they resolve to baseline or considered stable. It will be left to the investigator's clinical judgment to determine whether an adverse event is related and of sufficient severity to require the subject's removal from treatment or from the study. A subject may also voluntarily withdraw from treatment due to what he or she perceives as an intolerable adverse event. If either of these situations arises, the subject should be strongly encouraged to undergo an end-of-study assessment and be under medical supervision until symptoms cease or the condition becomes stable.

Pre-existing diseases, when worsening during study therapy, have to be considered as adverse events. They can lead to serious adverse events, if they meet the criteria described in section 7.1.3.

Intensity of adverse events will be graded using the National Cancer Institute Common Terminology Criteria for Adverse Events (CTCAE), version 4.03. If an adverse event occurs which is not described in the CTCAE version 4.03, the four-point scale below will be used.

Mild	Discomfort noticed but no disruption of normal daily activity
Moderate	Discomfort sufficient to reduce or affect daily activity
Severe	Inability to work or perform normal daily activity
Life-threatening	Represents an immediate threat to life

7.5 Laboratory Test Abnormalities

Laboratory test results will be recorded on the laboratory results pages of the CRF. In the event of unexplained abnormal laboratory test values, the tests should be repeated immediately and followed up until they have returned to the normal range and/or an adequate explanation of the abnormality is found. Laboratory test value abnormalities as such should not be reported on the AE page of the CRF as adverse events unless they are judged clinically significant by the investigator.

7.6 Pregnancy

Female patients must be instructed to immediately inform the investigator if they become pregnant during the study. The study treatment must immediately be stopped and the patient must be withdrawn from the study. Pregnancies occurring up to 6 months after the completion of the last treatment cycle must also be reported to the investigator. The investigator must report all pregnancies within 24 hours to GSO mbH. GSO mbH will forward all pregnancy reports to the sponsor within 24 hours. The investigator should counsel the patient; discuss the risks of continuing the pregnancy and the possible effects on the fetus. The patient should be monitored until the conclusion of the pregnancy.

Pregnancy occurring in the partner of a patient participating in the study should also be reported to the investigator, the sponsor and the CRO. The partner should be counseled and followed as described above.

7.7 Adverse Drug Reactions with Concomitant Medication

The investigators must be aware that for all concomitant medications the regulations of post-marketing reporting for suspected adverse drug reactions apply, i.e. reporting to the marketing authorization holder or the local regulatory bodies.

8 BIOSTATISTICS

8.1 Trial Design and Hypotheses

This is a single-arm trial to evaluate efficacy of Selinexor in patients with relapsed/ refractory AML by complete response rate (CR) or CRi), as defined by the revised recommendations of the International Working Group for diagnosis, standardization of response criteria in Acute Myeloid Leukemia for AML.

The trial tests the null hypothesis that the observed response rate is less or equal than the predefined limit of 30% versus the alternative hypothesis that the response rate is at least 60%.:

$$H_0 : p \leq p_0 \text{ against the alternative hypothesis } H_1 : p \geq p_1.$$

8.2 Sample Size Calculation

The sample size calculation is based on the evaluation of response rates according to Fleming using the A'Hern (Sample size tables for exact single-stage phase II designs. Statist. Med. 2001;20:859-866.) extension.

In Fleming's procedure two response levels p_0 and p_1 are specified:

- the largest response proportion p_0 which, if true, would clearly imply that the treatment does not warrant further investigations (except for other types of administration, e.g. in standardized combinations); and
- the minimum required response level p_1 that would imply the treatment warrants further investigations.

The following characteristics were specified

- $p_0 = 0.30$
- $p_1 = 0.60$
- $\alpha = 0.05$ (one-tailed) and
- $\beta = 0.10$

$N=25$ patients should participate in the study to ensure a power of $1-\beta=0.90$ for the discrimination of p_0 and p_1 . According to Fleming the null hypothesis should be rejected if at least

$$r = \left\lceil Np_0 + Z_{1-\alpha} \sqrt{Np_0(1-p_0)} \right\rceil + 1$$

responses are observed (x^* denotes the nearest integer to). With p_0 and N defined as above and $Z_{1-\alpha} = (1 - \alpha)$ -quantile of the normal distribution = 1.645 at least 12 responders should be observed to show the efficacy as postulated.

Using the same approach in the 15 additional patients, submitted to an adapted drug regimen, the power will be 80% to discriminate a $p_0=30\%$ (expected CR rate) from a $p_1=65\%$ (meaningful increase in CR rate), if 8 out of 14 completed patients are considered as responders, with a one-tailed alpha error of 5%.

Alternatively, the power will be 90% to discriminate a $p_0=30\%$ from a $p_1=70\%$ again if 8 out of 14 completed patients are considered as responders, with a one-tailed alpha error of 5%.

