
Sample size calculation
	
The sample size calculation is based on the evaluation of response rates according to Fleming for single-stage phase II designs. For the Fleming's procedure the two response levels p_0 (expected CR rate) and p_1 (meaningful increase in CR rate) are specified as $p_0=30\%$ and $p_1=60\%$:
 
$N=25$ patients should participate in the study to ensure a power of $1-\beta=0.90$ for the discrimination of p_0 and p_1. According to Fleming the null hypothesis should be rejected if at least
 $r = \left\lceil Np_0 + Z_{1-\alpha} \sqrt{Np_0(1-p_0)} \right\rceil + 1$ 
responses are observed ($\lceil x \rceil$ denotes the nearest integer to). With p_0 and N defined as above and $Z_{1-\alpha} = (1 - \alpha)$-quantile of the normal distribution = 1.645 at least 12 responders should be observed to show the efficacy as postulated.
 
Using the same approach in the 15 additional patients, submitted to an adapted drug regimen, the power will be 80% to discriminate a $p_0=30\%$ (expected CR rate) from a $p_1=65\%$ (meaningful increase in CR rate), if 8 out of 14 completed patients are considered as responders, with a one-tailed alpha error of 5%. Alternatively, the power will be 90% to discriminate a $p_0=30\%$ from a $p_1=70\%$ again if 8 out of 14 completed patients are considered as responders, with a one-tailed alpha error of 5%.

Accompanying baseline translational study (optional)	Leukemic blast cells will be isolated pre- and 24 hr post- a single Selinexor dose (60 mg) given at baseline (after registration and before first induction cycle). Blast cells will be used for leukemic stem cell gene expression profiling and in mouse model studies to define parameters associated with clinical responsiveness to Selinexor.
Data Monitoring Committee	An independent Data Monitoring Committee (DMC) will be implemented that reviews accumulating data of the clinical trial with respect to any potential safety issues, study progress and critical efficacy endpoints. The DMC will be an independent board consisting of 2-3 physicians with special expertise in AML. A physician is not allowed to participate in this clinical trial while serving on the DMC. The DMC will be supported by an independent statistician, if necessary. The DMC will review safety data, recovery times and efficacy of the clinical trial and support the interpretation of clinical trial results.

INFORMATION TO BE PROVIDED REGARDING SAES/PREGNANCY

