5.4 Removal of Patients from Treatment

Subjects will be free to discontinue treatment or withdraw from the study at any time, for any reason. Or they may be withdrawn/ removed if necessary in order to protect their health (see reasons for withdrawal below). It is understood by all concerned that an excessive rate of withdrawals can render the study uninterpretable; therefore, unnecessary withdrawal of subjects should be avoided. Patients who are withdrawn from the study will not be replaced.

Patients will be removed from further treatment for the following reasons:

- Disease progression
- Non-compliance
- Need of treatment with medications not allowed by the study protocol
- Patient no longer consents to participate in the study
- Intercurrent illness that interferes with study assessments
- Incidence or severity of AEs in this study indicates a potential health hazard to the patient
- Investigator discretion
- Pregnancy
- Termination of the study by the sponsor

If there is a medical reason for withdrawal of treatment, the patient will remain under the supervision of the investigator until the AEs have been resolved or declined to baseline values.

If a patient has failed to attend scheduled assessments in the study, the investigator must determine the reasons and circumstances as completely and accurately as possible.

In case of premature discontinuation of the study treatment, the investigations scheduled for the EOT and the follow-up visits should be performed, if possible. The CRF section entitled "End of Treatment" must be completed in all cases. Should a patient decide to withdraw, every effort will be made to complete and report the observations as thoroughly as possible. The investigator should contact the patient to determine as completely as possible the reason for the withdrawal. A complete final evaluation at the time of the patient's withdrawal should be made, with an explanation of why the patient is withdrawing from the study. If the reason for removal of a patient from the study is an adverse event or an abnormal laboratory test result, the principal specific event or test will be recorded on the case report form.

If a patient withdraws consent for further study treatment, the patient should still be followed for disease progression and overall survival. If a patient withdraws consent for further participation in the study, follow-up assessments will be discontinued.

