7.1 Intention-to-treat (ITT) set

The ITT set includes all subjects who have received study medication at least once and for whom efficacy data upon treatment are available.

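### The second cohort's decision rule and power are stated for 14 undefined completers, not for the 15 patients enrolled

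*Protocol*

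**What the plan says.** Protocol 8.2 (Sample Size Calculation) sizes the first cohort on 25 participating patients and rejects the null at 12 or more responders. It then turns to the flat-dose cohort: "Using the same approach in the 15 additional patients, submitted to an adapted drug regimen, the power will be 80% to discriminate a" null rate of 30% from 65%. The condition attached is "if 8 out of 14 completed patients are considered as responders, with a one-tailed alpha error of 5" per cent. A second statement, beginning "Alternatively, the power will be 90% to discriminate a" 30% rate from 70%, uses the same 8 of 14, again "with a one-tailed alpha error of 5" per cent. The synopsis repeats this.

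Neither place defines 'completed', gives a dropout rate that leads from 15 to 14, or says what happens if the number is not 14. Protocol 5.4 adds: "Patients who are withdrawn from the study will not be replaced".

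SAP 5 (Sample size considerations) keeps the 15 patients, the 30% and 65% rates and the 80% power. It gives neither the 14 nor the threshold of 8.

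On analysis sets, SAP 7.1 begins "The ITT set includes all subjects who have received study medication at least once" and goes on to require on-treatment efficacy data; Protocol 8.3.1 has the same definition. The only set defined by completing treatment is the per-protocol set (Protocol 8.3.2, SAP 7.2).

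**The concern.** The rule is presented as the same approach as in the first cohort, yet its denominator changes from participants to completers. Two things follow.

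First, a reader of SAP 5 will take the 80% as the power of an analysis of 15 patients, when it is the figure for 14.

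Second, completing treatment in relapsed or refractory AML depends on outcome. Protocol Appendix 7 classes deaths before the end of therapy as treatment failures, and early death is a secondary endpoint, so such cases are expected. A completer denominator can remove them. Nothing else in the plan clearly puts them back: the ITT set needs efficacy data, and SAP 8 says missing values will not be imputed. What is at stake is how the flat-dose result, reported separately under SAP 12.1, is judged against the 30% limit.

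**Working it through.** **Inputs.** From Protocol 8.2: p0 = 0.30; one-sided alpha 0.05; p1 = 0.65 (80% power) and 0.70 (90% power); rule of at least 8 of 14; 15 patients enrolled; first cohort N = 25, p1 = 0.60, at least 12 responders.

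**Formulas.** The protocol's threshold is r = nearest integer to [N·p0 + 1.645·√(N·p0·(1−p0))], plus 1. Exact error and power are P(X ≥ r) for X binomial (N, p), taking p = p0 for alpha and p = p1 for power.

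**Step 1: reproduce the plan.**
- First cohort, 12 of 25: alpha 4.4%, power 92.2% at 60%. This agrees with the plan.
- Second cohort, 8 of 14: alpha 3.1%, power 81.6% at 65% and 90.7% at 70%. This agrees. A search for the smallest exact design also returns 8 of 14 for both pairs of rates, so 14 is the exact design size.

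**Step 2: the protocol's formula at other denominators.**

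| N | Before rounding | Threshold r |
|---|---|---|
| 15 | 4.5 + 1.645 × √3.15 = 7.42 | 7 + 1 = 8 |
| 14 | 4.2 + 1.645 × √2.94 = 7.02 | 7 + 1 = 8 |
| 13 | 3.9 + 1.645 × √2.73 = 6.62 | 7 + 1 = 8 |
| 12 | 3.6 + 1.645 × √2.52 = 6.21 | 6 + 1 = 7 |
| 11 | 3.3 + 1.645 × √2.31 = 5.80 | 6 + 1 = 7 |

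**Step 3: exact properties.**

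| Rule | Alpha at 30% | Power at 65% | Power at 70% |
|---|---|---|---|
| 8 of 14 (stated) | 3.1% | 81.6% | 90.7% |
| 8 of 15 | 5.001% | 88.7% | 95.0% |
| 9 of 15 | 1.5% | 75.5% | 86.9% |
| 8 of 13 | 1.8% | 71.6% | 83.5% |

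The unrounded alpha of 8 of 15 is 0.050013, above 5% by about 0.00001.

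**Step 4: effect of leaving out non-completers.** Assume that all non-completers are non-responders and that the true rate among all 15 treated is 30%. The responders among completers are then the responders among all 15.
- Threshold held at 8: the error over 15 treated is at most P(X ≥ 8 | 15, 0.30) = 5.001%, however many are left out.
- Threshold recomputed on completers: with one or two left out it stays at 8, so nothing changes. With three or four left out (assumption) it falls to 7, and P(X ≥ 7 | 15, 0.30) = 13.1%.

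**The case against.** A reader might infer that, for the 15 treated patients, the stated 80% and 90% power fails. The documents do not support that. Their own formula gives 8 at N = 15, with power above both stated values. The shortfall to 75.5% and 86.9% appears only if an excess of 0.00001 in alpha is treated as disqualifying. Protocol 8.2 does cite an exact-design method, so a strict limit is a possible reading, but not the only one.

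A reader might also infer that the false-positive rate rises once more than one patient fails to complete. It does not. The threshold is 8 for 15, 14 and 13 patients, the protocol states a fixed 8, and it nowhere says to recompute. The 13.1% describes a procedure that the undefined denominator leaves open, not one that the protocol prescribes.

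The other side can add that 'completed' may mean only evaluable, and that planning for one unevaluable patient in 15 is ordinary. If that one patient counts as a failure, the 8-of-14 figures stand unchanged. The ITT set can itself fall below 15 because it needs efficacy data. The SAP reports a response rate with a 95% Wilson interval and does not carry the threshold, and enrolment closed in June 2016, so power cannot be changed.

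All of this stands, and it limits the point to an undefined denominator. It does not supply the missing definition, a rule for numbers other than 14, or agreement between Protocol 8.2 and SAP 5.

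**Conclusion.** The point holds as one of definition and consistency. No stated number is wrong for 14 patients. The stated figures are simply not those of the 15 patients to whom SAP 5 attaches the 80%. For those 15, the alpha and power are either 5.001%, 88.7% and 95.0% (threshold 8) or 1.5%, 75.5% and 86.9% (threshold 9), depending on whether alpha must be strictly at most 5%.

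The exclusion risk is conditional. Inflation to 13.1% needs at least three non-completers, all of them non-responders, and a threshold recomputed on completers. The documents give no dropout rate, so how likely this is cannot be judged from them. The binomial figures assume independent patients with a common response rate.

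**What to change.** In Protocol 8.2, the synopsis and SAP 5:
- State the second cohort's rule on all 15 treated patients, in place of 14 completed patients.
- State that patients without a documented response count as non-responders, in both cohorts. The documents currently give no such rule for either.
- Give the threshold with its exact properties: 8 of 15 (alpha 5.0%, power 89% at 65% and 95% at 70%), or 9 of 15 (alpha 1.5%, power 75% and 87%) if alpha must be strictly at most 5%.

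The SAP addendum shows that an initial analysis has already been run, so the choice of threshold should be dated and reported as a change from the plan.

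The cost is wording only, with no extra patients. The observed response rate will be slightly lower if any patient is unevaluable. With the 9-of-15 rule, the stated power falls below 80% and 90%.

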8.3 Evaluation Categories for Patients

A Data Review will be performed prior to the data base lock. In this meeting the patients will be assigned to the respective analysis set depending on the observed protocol deviations..

8.3.1 Intent-to-Treat Population

Intent-to-Treat Analysis Set (ITT): The ITT-population includes all subjects who have received study medication at least once and for whom efficacy data upon treatment are available.

8.3.2 Per Protocol Population

Per Protocol Set (PP): The PP population includes all patients who completed the treatment section (up to Visit 9) without any major protocol deviation.

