17.6 Appendix 6 – NCI-CTCAE version 4.03

17.7 Appendix 7- Response criteria in AML

Definitions of response criteria are based primarily on those given by Döhner et al.⁽¹⁾

Response criteria	Absolute Neutrophil count	Absolute Platelets count	Bone marrow Blasts (%)	Comments
Complete remission (CR)*	$>1.0 \times 10^9/L$ (1000/ μ L)	$>100 \times 10^9/L$ (100.000/ μ L)	<5	Absence of blasts with Auer rods; Absence of EMD; independence of red cell transfusion
CR with incomplete recovery (CRi) [†]	$<1.0 \times 10^9/L$ (1000/ μ L)	$<100 \times 10^9/L$ (100.000/ μ L)	<5	All CR criteria except for residual neutropenia or thrombocytopenia.
Morphologic leukemia-free state [‡]	NA	NA	<5	Absence of blasts with Auer rods; Absence of EMD; no hematologic recovery required
Partial remission (PR)	$>1.0 \times 10^9/L$ (1000/ μ L)	$>100 \times 10^9/L$ (100.000/ μ L)	5 to 25	Relevant in the setting of phase 1 and 2 clinical trials only; decrease of pretreatment bone marrow blast percentage by at least 50%
Cytogenetic CR (CRc) [§]	$>1.0 \times 10^9/L$ (1000/ μ L) or $<1.0 \times 10^9/L$ (1000/ μ L)	$>100 \times 10^9/L$ (100.000/ μ L) or $<100 \times 10^9/L$ (100.000/ μ L)	<5	Reversion to a normal karyotype at the time of morphologic CR (or CRi) in cases with an abnormal karyotype at the time of diagnosis; based on the evaluation of 20 metaphase cells from bone marrow
Molecular CR (CRm) ⁱ	No standard definition; depends on molecular target			

Treatment failure	
Resistant disease (RD)	Failure to achieve CR or CRi (general practice; phase 2/3 trials); or failure to achieve CR, CRi, or PR (phase 1 trials); only includes patients surviving ≥ 7 days following completion of initial treatment, with evidence of persistent leukemia by blood and/or bone marrow examination

Death in aplasia	Deaths occurring \geq 7 days following completion of initial treatment while cytopenic; with an aplastic or hypoplastic bone marrow obtained within 7 days of death, without evidence of persistent leukemia
Death from indeterminate cause	Deaths occurring before completion of therapy; or < 7 days following its completion; or deaths occurring ≥ 7 days following completion of initial therapy with no blasts in the blood, but no bone marrow examination available
Relapse [¶]	Bone marrow blasts $\geq 5\%$; or reappearance of blasts in the blood; or development of extramedullary disease

EMD extamedullary disease

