7.2 Per protocol (PP) set

The PP set will consist of all randomized subjects who completed the treatment section (up to Visit 9) with no relevant protocol violations, detailed in the subject classification document.

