12.2 Secondary efficacy variables

The secondary efficacy variables; rate of partial remissions, percentage of patients being transplanted after induction therapy and early death rate will be analysed using similar methods as with the primary analysis.

Overall survival, recurrence-free-survival and event-free survival will be analysed applying the Kaplan-Meier-method (KM). OS is calculated from the date of informed consent to the date of death, the patients still alive will be censored at the last date of follow-up. RFS is calculated from the date of informed consent to the date of recurrence or death, whichever occurs first, censoring patients who were alive without recurrence on the date of last follow-up visit. EFS is calculated from the date of CR/CRi until death or relapse, whichever occurs first. Patients are censored on the date of last follow-up visit if they are alive without relapse.

The survival curves will be displayed graphically for the overall population and by dosage schedule. In addition median survival and follow-up times (including interquartile range and 95 % CI if feasible) will be calculated.

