14.2.2 Secondary efficacy analysis

Table 14.2.2.1 Rate of partial remission overall and by dosing schedule (ITT)

Table 14.2.2.2 Rate of partial remission overall and by dosing schedule (PP)

Table 14.2.2.3 Percentage of patients being transplanted after induction therapy (ITT)

Table 14.2.2.4 Percentage of patients being transplanted after induction therapy (PP)

Table 14.2.2.5 Early death rate (ITT)

Table 14.2.2.6 Early death rate (PP)

Table 14.2.2.7 Summary statistics for overall survival endpoint (ITT)

Table 14.2.2.8 Summary statistics for overall survival endpoint (PP)

Table 14.2.2.9 Summary statistics for recurrence-free survival endpoint (ITT)

Table 14.2.2.10 Summary statistics for recurrence-free survival endpoint (PP)

Table 14.2.2.11 Summary statistics for event-free survival endpoint (ITT)

Table 14.2.2.12 Summary statistics for event-free survival endpoint (PP)

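### The per-protocol set excludes patients who die before Visit 9, yet the SAP tabulates early death rate, OS and RFS in that set

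*Protocol*

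**What the plan says.** Protocol 8.3.2 defines the PP set as "all patients who completed the treatment section (up to Visit 9) without any major protocol deviation". SAP 7.2 keeps the same condition: "completed the treatment section (up to Visit 9) with no relevant protocol violations". In both, completion is one requirement and freedom from important deviations is another.

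SAP 12 presents all efficacy data in both ITT and PP. Under heading 14.2.2, the table plan in SAP 19.2 includes "Table 14.2.2.6 Early death rate (PP"), and Tables 14.2.2.8 and 14.2.2.10 do the same for OS and RFS. SAP 12.2 says that "early death rate will be analysed using similar methods as with the primary analysis", which means a percentage with a Wilson 95% interval (SAP 12.1).

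For the time origin, SAP 12.2 states "OS is calculated from the date of informed consent to the date of death". RFS also starts at consent and counts death as an event.

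Protocol Appendix 7 lists "Deaths occurring before completion of therapy" under treatment failure, within the category of death from indeterminate cause.

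**The concern.** A patient who dies during induction has not completed the treatment section, whatever the data review decides about deviations. The set therefore selects on the outcome that three of its tables are meant to describe.

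For early death, the event itself removes the patient. For OS and RFS, each PP patient is credited with the time from consent to Visit 9, while anyone who died in that time is absent. This is immortal-time bias produced by the set definition.

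At stake is how supportive tables are read. A low PP early death rate, printed with a confidence interval beside the ITT figure, looks like an estimate from patients treated as planned. In fact it reflects the entry rule. Early death is a planned secondary endpoint and bears on safety.

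**Working it through.** **The plan's own figures.** None is attached to this point. The design figures reproduce: 25 × 0.30 + 1.645 × √(25 × 0.30 × 0.70) = 11.27, rounded to 11, plus 1 gives 12. Exact binomial error for 12 of 25 is 0.044, with power 0.922 at 60%. For 8 of 14 the error is 0.031, with power 0.816 at 65% and 0.907 at 70%. Nothing below changes these.

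**Where Visit 9 falls.** The schedules (Protocol Table 2, SAP 19.1) do not number visits, so two counts are assumed.
- Screening, baseline, six Selinexor dosing days (2, 4, 9, 11, 16, 18) and end of cycle: 1 + 1 + 6 + 1 = 9, the end of cycle 1. The baseline visit is optional.
- Schedule columns with two induction cycles: screening, baseline, 2 × (during, end), consolidation, maintenance, end of treatment: 2 + 4 + 3 = 9, the end of treatment.

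On either count, a patient who dies before the marrow at the end of cycle 1 is out.

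**Early death rate.** Assumptions: d deaths before Visit 9 among 40 treated, an early-death window ending by Visit 9, and no other exclusions. PP then shows 0/(40 − d). For zero events the Wilson upper limit is z²/(n + z²), with z = 1.96.

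| d | All treated (Wilson 95% CI) | PP | PP upper limit |
|---|---|---|---|
| 0 | 0% (upper limit 8.8%) | 0/40 | 8.8% |
| 2 | 5.0% (1.4 to 16.5) | 0/38 | 9.2% |
| 4 | 10.0% (4.0 to 23.1) | 0/36 | 9.6% |
| 6 | 15.0% (7.1 to 29.1) | 0/34 | 10.2% |

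**OS.** Assumptions: a constant hazard from first dose with median m, and Visit 9 at L = 28 days (28/30.44 = 0.92 months) or 56 days (1.84 months). The share excluded is 1 − 0.5^(L/m), and the median among those left is m + L. The interval from consent to first dose is guaranteed in any treated set, so it does not alter the difference L.

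| m (months) | Excluded, day 28 / 56 | PP median, day 28 / 56 |
|---|---|---|
| 4 | 14.7% / 27.3% | 4.9 / 5.8 |
| 6 | 10.1% / 19.1% | 6.9 / 7.8 |
| 8 | 7.7% / 14.7% | 8.9 / 9.8 |
| 12 | 5.2% / 10.1% | 12.9 / 13.8 |

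At day 28, medians of 4 to 12 months imply 40 × 0.147 = 5.9 down to 40 × 0.052 = 2.1 deaths, which is why 2 to 6 were tabulated.

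**PP response rate.** Deaths before Visit 9 leave the denominator. CR/CRi patients who end treatment for transplant after one cycle (Protocol 3.1.3) may also fail the completion condition. With an assumed 18 responders of 40 (45.0%), dropping 4 deaths gives 18/36 = 50.0%. Dropping 4 such responders as well gives 14/32 = 43.8%. The direction is open.

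**EFS.** SAP 12.2 starts it at CR/CRi. The effect is weaker there, though a responder who dies before Visit 9 would still be lost.

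**The case against.** The strongest reply is that little depends on these tables. Each has an ITT counterpart (14.2.2.5, 14.2.2.7, 14.2.2.9), the Kaplan-Meier figures and the transplant-censored summaries are ITT only, and deaths with reasons appear in Table 14.3.2.9. Excluding non-completers from a PP set is conventional. This stands, and it confines the point to supportive tables. It does not rescue an early-death table that cannot register the earliest deaths.

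The set might also be applied differently from its wording. SAP 7.2 speaks of randomized subjects in a non-randomized trial, which suggests template text, and the subject classification document is not available. It could treat death as completion, but neither document says so. Both tie the review's assignment to deviations or violations, and completion is a separate condition.

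The size is also uncertain, and that objection stands in full. A reader might infer that the PP early death rate must be zero. It is zero only if the early-death window ends by Visit 9; with a longer window, later deaths would still appear. Nor do the illustrative figures show incompatible intervals: at 4 deaths the PP interval (0 to 9.6%) lies below the all-treated estimate of 10.0%, but it overlaps the all-treated interval (4.0 to 23.1%).

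Finally, the planned comparator is ITT rather than all treated patients. ITT requires on-treatment efficacy data (Protocol 8.3.1, SAP 7.1) and may itself lose deaths before the first marrow, so the printed gap between PP and ITT could be smaller than shown.

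**Conclusion.** The conflict is real and minor. As written, the plan omits deaths before Visit 9 from the PP early death rate and builds guaranteed survival time into PP OS and RFS. The direction for these three tables follows from the definitions, provided that death is not treated as completion. The size does not, because the death count, Visit 9 and the early-death window are missing; the figures above rest on assumed values. With no deaths before Visit 9, the early-death table is unaffected.

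Two stronger readings are not supported. A reader might infer that the PP response rate is inflated, but one-cycle responders leaving for transplant may be excluded too, so no direction can be claimed. A reader might also infer that the response criterion of 12 of 25 or 8 of 14 is compromised. Nothing in the PP rule touches those counts or the ITT tables.

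**What to change.** Issue a dated SAP addendum that does the following.

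1. Delete Tables 14.2.2.6, 14.2.2.8 and 14.2.2.10, and add a matching exception to SAP 12.
2. Report early death rate, OS and RFS in all patients who received at least one dose, which is the Protocol 8.3.3 set. Keeping only the ITT versions would not be enough, since the efficacy-data requirement could drop the same early deaths. SAP 7.3 is not a substitute either, because it adds a subsequent safety measurement.
3. Footnote the PP response tables (14.2.1.2 and 14.2.1.4) with the number of treated patients excluded because they died before Visit 9, and the number of CR/CRi patients excluded because they left for transplant after one cycle. The date taken as Visit 9 has to be stated for these counts to be readable.

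Protocol 8.3.2 need not be rewritten, so no protocol amendment is required. The cost is three fewer supportive tables. The SAP Addendum of April 2018 (Section 3) shows that an initial analysis has already been run, so the change would come after results were seen, and the study report should disclose this. No new patient data are needed, and no patient's treatment changes.
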